### **3. STUDY DESIGN**

The proposed research will determine feasibility and acceptability of investigating the eMMB and AC interventions to reduce pain and other surgical outcomes through an exploratory stratified randomized controlled pilot study among 31 women undergoing surgery for suspected gynecologic malignancies.

Participants enrolled will be randomized 1:1 to eMMB or AC. Allocation will stratified by cancer type (i.e., ovarian or uterine) and invasiveness of the planned surgical procedure type (i.e., laparotomy or robotic). Patient-reported assessments will be conducted at four time points: before surgery (baseline), one day after surgery, two weeks after surgery and 4 weeks after surgery. Participants will also be asked to complete daily assessments of outcomes and adherence to home practice of the intervention and wear a wrist actigraphy device for up to one week before and one week following surgery. In addition, medical records will be reviewed, treatment fidelity observed, and an interview conducted at a follow-up clinic visit or by telephone. We will also track recruitment, adherence to the videoconference intervention, any other contact with interventionists, and completion of assessments. Our findings will inform an efficacy trial of the eMMB for improving surgical outcomes of adults who undergo surgery for a suspected gynecologic malignancy.

In-person MMB and AC interventions investigated in our Preliminary Research will be adapted in the proposed research to be implemented by eHealth. The initial dose of the eMMB and AC interventions will include a call to invite participants to initiate additional guidance upon request prior to surgery and a meeting with the participant via videoconferencing the day following surgery. Participants will also be given a self-directed video to be used before surgery and daily for two weeks following surgery in the eMMB group and diaries to complete daily in the AC group.

The approximately 20-minute eMMB will teach: (a) Awareness Meditation - noticing the current state of the body, emotions, thoughts, energy, and breath; (b) Movement – gentle movements coordinated with the breath; (c) Breathing and Relaxation - placing the hands above the navel and noticing them rise and fall with a focus on slightly extending the exhale; (d) Awareness Meditation – 5 minutes of awareness of noticing the natural breath without changing it to enhance mindfulness. The intention to maintain attention or mindfulness (sthira), comfort and ease (sukha) is highlighted throughout the eMMB.

An AC group focused on providing caring attention will be employed to account for the added time, attention, interaction with an interventionist, and efficacy expectations of the eMMB. In addition, the interventionist will ask patients to write brief diary entries daily at home as used in previous research and our current study. The AC will be implemented by an individual with experience working in a medical setting who will be trained to create and maintain a relationship by using techniques such as active listening, reflection of statements, and avoiding negative judgments.

The total length of time each participant will be on study is approximately 4 weeks. The enrollment period for the trial is expected to continue for 12 months.

## 4. SELECTION AND ENROLLMENT OF PARTICIPANTS

We will seek approval from the Institutional Review Board (IRB) prior to implementing the proposed study and take precautions to ensure adequate protection of human subjects. Recruitment of women scheduled to undergo surgery for a suspected gynecologic malignancy at the Wake Forest Baptist Comprehensive Cancer Center (WFBCCC) will be facilitated by [name] (Co-Investigator). To increase homogeneity, only the most prevalent gynecologic malignancies will be recruited (i.e. uterine, ovarian) that occur in only women. We chose this target population because adult women undergoing surgery for suspected cancer are at particularly high risk for experiencing chronic pain. In addition, this sample reduces variability due to sex differences in pain tolerance and response to pain medication. There are multiple theories that may explain these differences. Of particular note is the “vulnerability theory”, which posits that sex hormones affect the nervous system’s and psychological responses to pain.

### 4.1 Inclusion Criteria

Participants must meet all of the inclusion criteria to participate in this study.

- Adult females ( $\geq 18$  years of age)
- Scheduled for an abdominal gynecological surgery (i.e. uterine, ovarian) to remove a suspected malignancy
- Have an Eastern Cooperative Oncology Group (ECOG) performance status of  $\leq 1$
- Cognitively able to complete assessments as judged by the study team
- Able to understand, read and write English.

## 4.2 Exclusion Criteria

All candidates meeting any of the exclusion criteria listed below at baseline will be excluded from study participation:

- Have schizophrenia or any other psychotic disorder;
- Have a diagnosed sleep disorder including untreated obstructive sleep apnea, periodic limb movement disorder, or restless leg syndrome.

## 4.3 Study Enrollment Procedures

Individuals scheduled to undergo surgery for suspected gynecologic malignancies (i.e., uterine, ovarian) will be recruited from the Wake Forest Baptist Comprehensive Cancer Center (WFCCC). To identify potential patients, the Project Manager will screen appointment lists and communicate with attending physicians regarding patients' potential eligibility for the trial. Subject recruitment will be documented in a Screening Log including reasons for ineligibility, eligible patients approached, number who declined participation, and number successfully recruited.

If the patient is interested and referred by the physician, the Project Manager will approach or call interested patients prior to surgery to explain the protocol, answer questions, determine eligibility, and discuss informed consent. After making sure the patient clearly understands the study procedures and agrees to follow them, the patient will be asked to sign the informed consent form electronically or in person. If signed electronically, patients will be asked to send the form back to us by a secure means (e.g., REDCap). In the case that the patient is consented electronically, either a hard copy or email attachment of the informed consent document will be provided to the participant. (Appendix A: Informed Consent Document). The original copy will be kept in the participant's file. Each participant will be asked to separately agree to be audio recorded for the study, which will not affect their ability to participate. If they do consent to be videotaped, they are told in the consent form that they can ask not to be included in the filming or withdraw their consent to be videotaped at any time. These videos are focused on the interventionist for the sole purpose of increasing treatment fidelity.

Eligible participants enrolled in the study will be randomized after baseline assessments to the eMMB or AC prior to surgery.

*Randomization.* Participants enrolled will be randomized 1:1 to eMMB or AC. Allocation will be computer-generated, stratified by cancer type (i.e. ovarian, uterine), and concealed by [name] (Biostatistician). Study team members will not know group assignment when enrolling participants. The Project Manager and PI who assign participants to interventions will be made aware of group assignment after a participant has provided informed consent. The Clinical Studies Staff member who will collect primary outcome data will be blinded to group assignment. Participants will be informed that they could be randomly assigned to 1 of 2 different supportive treatments with a general description of what they will involve (i.e., counseling,

gentle movement, writing, and/or relaxation strategies) and will be asked not to discuss study procedures with their treating surgeon, medical staff, or research personnel. Thus, participants and healthcare providers will also be blinded to randomization.

## 5. STUDY INTERVENTIONS

### 5.1 Interventions, Administration, and Duration

**Active Intervention.** The Mindful Movement and Breathing (eMMB) intervention will be administered individually via telephone and video conference for initial guidance and is primarily intended to be self-directed (video). We considered the style, delivery, components of the intervention, specific class sequences, facilitation of home practice, dose, dealing with modifications, selection of instructors, and measurement of intervention fidelity, as recommended in the development of a yoga intervention for a randomized trial.

*Style.* The content of the eMMB was informed by the PI's training from the Integral Yoga Academy's Yoga for People with Cancer Teacher Training and Urban Zen Integrative Therapy training, and was refined for this study by consulting with expert yoga therapists from the Krishnamacharya tradition (led by [name], Consultant) and an expert in instructing mindfulness for reducing pain ([name], Co-Investigator). Expert yoga therapists from the Krishnamacharya tradition are ideal for informing this approach since this tradition systematically selects yoga practices based on therapeutic targets (e.g., pain) and places an emphasis on daily home practice. Furthermore, the eMMB aims to promote mindfulness and relaxation.

*Delivery components and class sequence.* The approximately 20-minute eMMB will teach: (a) Awareness Meditation - 2 minutes of noticing the current state of the body, emotions, thoughts, energy, and breath. Brief meditation has been shown to be effective for decreasing pain, sleep disturbance and psychological distress and will increase mindfulness to facilitate safe physical movements; (b) Movement – 10 minutes of gentle movements coordinated with the breath also aim to enhance mindfulness to reduce pain, facilitate bowel movement (to prevent ileus) and blood flow (to prevent deep venous thrombosis); (c) Breathing and Relaxation - 3 minutes of placing the hands above the navel (rather than on the belly to avoid discomfort) and noticing them rise and fall with a focus on slightly extending the exhale to induce relaxation. This practice aims to improve lung capacity (to reduce pulmonary compromise) and reduce pain, sleep disturbance and psychological distress; (d) Awareness Meditation – 5 minutes of awareness of noticing the natural breath without changing it to enhance mindfulness. The intention to maintain attention or mindfulness (*sthira*), comfort and ease (*sukha*) is highlighted throughout the eMMB. We also propose that teaching these skills will increase self-efficacy for pain management through providing successful pain management experiences.

*Dealing with modifications.* The movements were chosen to be appropriate following surgery. Each session contains the same content, but the number of repetitions and the magnitude of movements are self-adapted based on how the participant is feeling. Any medical restrictions are within the scope of the eMMB.

*Selection of instructors.* Yoga instructors (one primary, two back-ups) will be contracted employees, accredited (i.e., certified as at least 200-hour-level teachers with the Yoga Alliance), and experienced teaching patients with medical conditions.

**Dose and Implementation of eMMB.** A 20-minute eMMB video will be saved as a local file on study tablets and/or will be accessible via the internet (participants will be given the option to receive a link to the study video via email). Participants will also be given a written description of the eMMB practice. Although guidance (i.e., supportive accountability) is important in promoting adherence to eHealth interventions, one study of a stress-management intervention found that adherence-focused guidance (e.g., email reminders, guidance upon request by participants) was as good as more resource intensive content-focused guidance. Thus, in the proposed study, participants will be given the video before surgery and asked to watch it at least once before the procedure. The yoga instructor will call participants before surgery to initiate additional guidance upon request at any time throughout the study and meet with the participant via videoconferencing using Cisco WebEx in the privacy of the hospital room the day following surgery (postoperative day 1 or as soon as feasible). Cisco WebEx supports compliance with the administrative and physical safeguards sections of the final HIPAA Security Rules. The yoga instructors' contact information will be provided with the intervention materials indicating their hours of availability and expected response time. Instructors will attempt to call participants 2 times prior to surgery without leaving a message. Participants will be given an option to communicate with instructors via text messaging from a Medical Center device to increase convenience of scheduling. Meeting live via videoconference will allow yoga instructors to see participants and ensure that they feel comfortable completing the movements postoperatively. The videoconferencing session will be facilitated by the Project Manager and will be audio recorded. If problems transmitting the live intervention occur or it is not possible to complete the intervention in the clinical setting, we will have the interventionist lead the intervention and answer questions by telephone. Participants will be asked to continue to use the video daily for two weeks following surgery and as long as they choose thereafter. The Project Manager will monitor patient-reported self-directed use of the video and call to check in with all participants after the first two days. This dose of content-focused guidance is similar to that found to be effective in other brief or primarily self-directed interventions. For example, hypnosis implemented during one 15-minute pre-operative in-person session, with instructions for how patients could use hypnosis on their own, reduced postoperative pain in women undergoing breast cancer surgery. A self-directed approach may also empower participants to establish self-regulation strategies.

**Attention Control (AC).** An AC group focused on providing caring attention will be employed to account for the added time, attention, interaction with an interventionist, and efficacy expectations of the eMMB as recommended for the study of mind-body practices and used in previous studies. In addition, the interventionist will ask patients to write brief diary entries once before surgery and daily for two weeks following surgery. A diary form will be saved as a local file on study tablets via the

REDCap App and/or will be accessible via the internet (participants will be given the option to receive a link to the study diary via email). Participants will also be given the option to complete a paper diary. The Project Manager will monitor patient-reported self-directed diary completion and call to check in with participants if they have not completed the diary after the first two days. The AC will not include instruction of movement, meditation or breathing practices, which are the active ingredients of the eMMB. The format for interactions with a professional, amount of recommended home practice, and home assessments will be matched to the eMMB. The AC interventionist will call participants before surgery to initiate additional caring attention upon request at any time throughout the study and meet with the participant via videoconferencing following surgery (postoperative day 1 or as soon as feasible) for 30 minutes to provide caring attention. The videoconferencing session will be facilitated by the Project Manager and will be recorded. The AC will be implemented by an individual with experience working in a medical setting who will be trained to create and maintain a relationship by using techniques such as active listening, reflection of statements, and avoiding negative judgments. S/he will utilize standardized instructions to prompt the patient as adapted from previous studies: “*What were some of the events or circumstances that affected you in the past two weeks?*” Patients will be encouraged to “*discuss one experience at a time, even if it means talking about the same experience each session. However, if you find that you have discussed it in adequate detail, please move on to a new topic.*” The instructions for daily diary entries will be, “*What were some of the events or circumstances that affected you in the past day? Think back over the past day and write down on the lines below up to five events that had an impact on you.*”

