### **9.5.1 Primary Outcome**

The primary study outcome is feasibility (i.e., recruitment, adherence, assessment completion, and retention rates)

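### Section 5.1 gives the two arms different Project Manager check-in rules, although the control arm is meant to account for time and attention

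*Combined protocol and SAP*

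**What the plan says.** Section 5.1 describes the check-in call twice, once per arm, with the same caller and different triggers.

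- **eMMB (Dose and Implementation of eMMB).** The Project Manager monitors self-reported video use and will "call to check in with all participants after the first two days". Use of the video is not a condition.
- **AC (Attention Control).** The Project Manager monitors diary completion and will "call to check in with participants if they have not completed the diary after the first two days". Non-completion is the trigger.

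The Attention Control text says that the AC group "will be employed to account for the added time, attention, interaction with an interventionist, and efficacy expectations of the eMMB". It adds: "The format for interactions with a professional, amount of recommended home practice, and home assessments will be matched to the eMMB". Section 9.1 repeats the purpose, listing attention from a professional among the non-specific effects that the control is there to cover.

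Adherence and retention are part of the primary feasibility outcome (Section 9.5.1). Section 9.6 tests both against 70% and, in exploratory analyses, compares non-adherent participants and drop-outs by intervention group, among other factors. The contact to be tracked in Sections 5.4 and 6.2.4 is additional contact with the interventionists. Project Manager calls are not named.

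**The concern.** An attention control is useful to the extent that non-specific contact is alike in the two arms. A call made to everyone in one arm and only to non-completers in the other is a difference in contact written into the procedures.

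On the protocol's own reasoning the call is not neutral. The eMMB paragraph describes guidance as important for adherence to eHealth interventions, and Section 2.1 sets out a supportive accountability model in which human contact can influence adherence.

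Two uses of the data are affected. The pooled adherence and retention rates would combine two prompting rules. A difference between arms in non-adherence or drop-out could not be assigned to the content of the intervention rather than to the extra call. Section 1.2 also expects the pilot to yield a manual of procedures for an efficacy trial, so an unnoticed mismatch could carry forward to a trial in which the contrast between arms is the main question.

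**Working it through.** **1. The two readings.**

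| Reading of the eMMB sentence | eMMB rule | AC rule | Consequence |
|---|---|---|---|
| All eMMB participants | everyone called | only non-completers called | contact differs by arm, against the AC's stated purpose |
| All participants in the trial | everyone called | everyone called by one sentence, only non-completers by the other | direct contradiction |

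The first reading is the more natural one: the sentence sits in the eMMB dose paragraph and concerns video use, and the AC has its own rule. The second is possible, because other sections use the phrase for both arms. Either way the text needs reconciling.

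**2. Number of calls under the first reading.** Inputs: N = 31 (Section 9.2) and 1:1 allocation (Section 3), so 15 or 16 per arm. The documents do not give the share *q* of AC participants who have not completed the diary at the check. I assume 10% to 50%.

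- eMMB calls = *n* = 15 or 16.
- AC calls = *n* × *q*:

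| *q* | *n* = 15 | *n* = 16 |
|---|---|---|
| 10% | 1.5 | 1.6 |
| 30% | 4.5 | 4.8 |
| 50% | 7.5 | 8.0 |

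- AC participants not called = *n* × (1 − *q*), from 15 × 0.5 = 7.5 to 16 × 0.9 = 14.4. This is also the number of extra calls if the universal rule were extended to the AC.

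**3. Who receives the extra contact.** As written, non-completers are called in both arms. The difference lies among participants who are already doing the home practice: they are called in eMMB and not in AC.

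**4. What the pilot could show about a consequence.** Section 9.2 states a precision of ±18% with a two-sided 95% interval. The normal-approximation half-width at a proportion of 50% is 1.96 × √(0.25/31) = 0.176, which reproduces it. The same method for a difference between arms of 15 and 16, at 70% adherence in each, gives 1.96 × √(0.21/15 + 0.21/16) = 0.323, or about ±32 points. At 50% it is about ±35 points. The pilot therefore could not tell a moderate effect of one call from chance. The difference in rules is nevertheless systematic, and a larger sample would not remove it.

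**5. Net attention.** The AC videoconference is "for 30 minutes to provide caring attention". For the other arm the text reads "The approximately 20-minute eMMB will teach", and the length of the live eMMB session is not stated separately. Time in session may therefore favour the AC while the check-in call favours eMMB. The direction of the total is unclear.

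**The case against.** The strongest case on the other side has four parts.

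- **What is matched.** Section 5.1 matches the format of interactions with a professional, not the number of contacts, and the caller is the Project Manager rather than an interventionist. This stands, so the matching sentence alone does not decide the point. The stated purpose of accounting for time and attention (Sections 5.1 and 9.1) still does.
- **Adherence.** A reader might infer that adherence differs by arm by design. The documents do not support that. They show different prompting and call contact, and a different achieved adherence is only a possible result. Non-completers are called in both arms, and both arms also receive an evening survey prompt for up to a week before and a week after surgery (Section 6.2), which dilutes the effect of one call.
- **The comparison by arm.** A reader might call this comparison confounded. Arms are randomised and each call rule belongs to its arm's package, so the comparison of packages remains fair. It is also exploratory, the tests in Section 9.6 are one-sample tests, and Section 9.2 says that the pilot is not designed to assess an effect of eMMB. What is lost is attribution to content.
- **Drafting.** The difference may be loose wording rather than intent, and neither sentence says when the first two days begin. This stands too, and is a further reason to reconcile the sentences.

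**Conclusion.** The point holds as an unreconciled difference in check-in rules. On the natural reading, contact and prompting differ by arm: 15 or 16 eMMB participants are due a call, against about 1.5 to 8 in AC, which rests on an assumed 10% to 50% diary non-completion. On the other reading, Section 5.1 contradicts itself.

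An effect on adherence or retention is plausible and unproven, and the net direction of attention is not known. No efficacy claim is at stake. The point still deserves action: adherence and retention are primary feasibility measures, the comparison by arm cannot separate content from the call, and the contact named for tracking would not let the calls be tabulated afterwards.

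**What to change.** Reconcile the two sentences in Section 5.1 so that one check-in rule, chosen by the team, applies to both arms, and state when the first two days begin. In Sections 5.4 and 6.2.4, add Project Manager check-in calls to the contact that is tracked, and tabulate them by arm alongside interventionist contact.

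The cost is one sentence and one log field. If the universal rule is chosen, the AC arm needs about 7 to 14 extra short calls under the assumed 10% to 50% non-completion. If the conditional rule is chosen, there are fewer calls overall.
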